## 8.4.3.2. Exposure During Breastfeeding

Scenarios of exposure during breastfeeding must be reported, irrespective of the presence of an associated SAE, to Pfizer Safety within 24 hours of the investigator's awareness, using the CT SAE Report Form. An exposure during breastfeeding report is not created when a Pfizer drug specifically approved for use in breastfeeding women (eg, vitamins) is administered in accord with authorized use. However, if the infant experiences an SAE associated with such a drug's administration, the SAE is reported together with the exposure during breastfeeding.

## **8.4.3.3.** Occupational Exposure

An occupational exposure occurs when, during the performance of job duties, a person (whether a healthcare professional or otherwise) gets in unplanned direct contact with the product, which may or may not lead to the occurrence of an AE.

An occupational exposure is reported to Pfizer Safety within 24 hours of the investigator's awareness, using the CT SAE Report Form, regardless of whether there is an associated SAE. Since the information does not pertain to a subject enrolled in the study, the information is not recorded on a CRF; however, a copy of the completed CT SAE Report Form is maintained in the investigator site file.

## 8.4.4. Medication Errors and Lack of Efficacy

Other exposures to the investigational product under study may occur in clinical trial settings, such as medication errors and lack of efficacy.

Safety Event	Recorded on the CRF	Reported on the CT SAE Report Form to Pfizer Safety Within 24 Hours of Awareness
Medication errors and lack of efficacy	All (regardless of whether associated with an AE)	Only if associated with an SAE

#### 8.4.4.1. Medication Errors

Medication errors may result from the administration or consumption of the investigational product by the wrong subject, or at the wrong time, or at the wrong dosage strength.

Medication errors include:

- Medication errors involving subject exposure to the investigational product;
- Potential medication errors or uses outside of what is foreseen in the protocol that do or do not involve the participating subject;
- The administration of expired investigational product;

- The administration of an incorrect investigational product;
- The administration of an incorrect dosage;
- The administration of investigational product that has undergone temperature excursion from the specified storage range, unless it is determined by the sponsor that the investigational product under question is acceptable for use.

Such medication errors occurring to a study participant are to be captured on the medication error page of the CRF, which is a specific version of the AE page.

In the event of a medication dosing error, the sponsor should be notified immediately.

Whether or not the medication error is accompanied by an AE, as determined by the investigator, the medication error is recorded on the medication error page of the CRF and, if applicable, any associated AEs, serious and nonserious, are recorded on an AE page of the CRF.

Medication errors should be reported to Pfizer Safety within 24 hours on a CT SAE Report Form only when associated with an SAE.

#### 8.4.4.2. Lack of Efficacy

Lack of efficacy in an approved indication (approved 13vPnC indication in this age group) should be reported as an SAE to Pfizer Safety.

#### 8.5. Medical Device Complaint Reporting Requirements

All medical device complaints, regardless of whether the medical device complaint is associated with an AE, will be recorded on the applicable pages within the CRF. This includes potential incidents or malfunctions associated with the use of a medical device product. An incident or malfunction is an event that might have led to death or serious deterioration in health, or if it occurred again might lead to death or serious deterioration in health.

Pfizer is to be notified of all medical device complaints within 24 hours of the investigator's awareness of the event.

## 9. DATA ANALYSIS/STATISTICAL METHODS

Detailed methodology for summary and statistical analyses of the data collected in this study is outlined here and further detailed in a statistical analysis plan (SAP), which will be maintained by the sponsor. The SAP may modify what is outlined in the protocol where appropriate; however, any major modifications of the primary endpoint definitions or their analyses will also be reflected in a protocol amendment.

#### 9.1. Sample Size Determination

The study size is not based on any formal statistical hypothesis test. Approximately 230 infants per vaccine group are planned to be randomized. No hypothesis tests between vaccine groups are planned; therefore, no power calculations for comparison of vaccine groups are included.

With 230 subjects per arm, the probabilities of observing at least 1 AE, local reaction, or systemic event where the true rate is 0.5%, 1%, and  $\geq 5\%$  are presented in Table 4.

Table 4. Probability of Observing at Least 1 AE, Local Reaction, or Systemic Event by Assumed True Event Rates

Sample Size	Assumed True Event Rate	e of at Least 1 AE, Local Ro	eaction, or Systemic Event
	0.5%	1%	≥5%
N=230	0.684	0.901	>0.999

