### 2.1.2. Primary Endpoints

- Proportions of subjects reporting prompted local reactions (redness, swelling, and pain at the injection site) within 7 days of each dose.
- Proportions of subjects reporting prompted systemic events (fever, decreased appetite, irritability, and drowsiness/increased sleep) within 7 days of each dose.
- Proportions of subjects reporting adverse events (AEs) from Dose 1 to 1 month following Dose 3 and from Dose 4 to 1 month following Dose 4.

• Proportions of subjects reporting serious adverse events (SAEs) and newly diagnosed chronic medical conditions (NDCMCs) from Dose 1 to 6 months following Dose 4.

[figure not shown]

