### 3.1. Duration of Subject Participation

Each subject will participate in the study for approximately 16 months.

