### 3.3. Number of Subjects

Approximately 460 subjects will be randomized (230 subjects per arm). Assuming a 15% dropout rate, approximately 200 subjects would be evaluable for immunogenicity. Subjects who withdraw or are withdrawn from the study after randomization will not be replaced, regardless of the reason for withdrawal.

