# 9.4. Safety Analysis

All safety analyses will be performed using the safety population.

Descriptive statistics for local reactions and systemic events from Day 1 to Day 7 will be presented by severity and cumulatively across severity levels. Descriptive statistics will include proportions of subjects with the indicated endpoint and the associated Clopper-Pearson 95% CIs. Vaccine groups will be compiled separately.

Descriptive statistics for local reactions and systemic events will be compiled separately for each dose. The same descriptive statistics will be compiled across all 4 doses.

AEs (including nonserious AEs, SAEs, and NDCMCs) will be compiled over 2 intervals: from Dose 1 to 1 month following Dose 3 and from Dose 4 to 1 month following Dose 4. SAEs and NDCMCs will be summarized from Dose 1 until 6 months after Dose 4. The descriptive statistics for AEs will be summarized as the number and percentage of subjects reporting at least 1 event of each preferred term with the associated Clopper-Pearson 95% CIs, arranged by system organ class.

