4.1. Safety Analysis Population

The **overall safety population** will include all subjects who receive at least 1 dose of study vaccine (20vPnC or 13vPnC) and have safety data reported in the study. Subjects will be assigned to vaccine group corresponding to the vaccine actually received. The safety population will be the analysis population for safety and reactogenicity endpoints.

Separate safety populations will be defined for each vaccination as follows:

Dose 1 to Dose 3 Safety Population - Subjects receiving Dose 1 and having safety data between Dose 1 and the blood draw visit 1 month after Dose 3

Dose 4 Safety Population - Subjects receiving Dose 4 and having safety data between Dose 4 and 6 months after Dose 4

If a subject's actual vaccine dose varies within a particular safety population (eg, overall or Dose 1 to Dose 3), the subject data will be either analyzed for any by-dose presentation, or data will be presented in listings as appropriate.

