6. ANALYSES AND SUMMARIES

6.1. Primary Endpoints

6.1.1. Local Reactions

6.1.1.1. Primary Analysis

Endpoints: Proportions of subjects reporting prompted local reactions (redness, swelling, and pain at the injection site) within 7 days of each dose

- Analysis time points: Within 7 Days Dose 1; Within 7 Days Dose 2; Within 7 Days Dose 3; Within 7 Days – Dose 4
- Analysis population: Dose 1 to Dose 3 safety population for Doses 1 to 3, Dose 4 safety population for Dose 4
- Analysis methodology: Descriptive statistics
- Supporting objective: Primary Objective

Reporting results:

Proportions of subjects reporting prompted local reactions will be summarized by maximum severity level. The percentage (%) and the numerator (n) and the denominator (N) used in the percentage calculation, and corresponding 95% Clopper-Pearson CI will be presented for each vaccine group at all time points. The same descriptive statistics will be compiled across all 4 doses.

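### Does Table 4's detection probability at 230 per arm need a separate figure for the Dose 4 safety endpoints?

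*Protocol*

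**What the plan says.** Protocol Section 9.1 states that the study size does not come from a hypothesis test. Its only quantitative support is Table 4, introduced with "With 230 subjects per arm, the probabilities of observing at least 1 AE, local reaction, or systemic event". The table has one row, labelled N=230, and mentions no dose or reporting interval.

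The primary endpoints in Protocol Section 2.1.2 are split by time. Local reactions and systemic events are counted after each dose, and AEs are counted "from Dose 1 to 1 month following Dose 3 and from Dose 4 to 1 month following Dose 4". Protocol Section 9.4 adds: "Descriptive statistics for local reactions and systemic events will be compiled separately for each dose". It also asks for the same statistics across all four doses.

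For local reactions, SAP Section 6.1.1.1 sets the analysis population as "Dose 1 to Dose 3 safety population for Doses 1 to 3, Dose 4 safety population for Dose 4". SAP Section 4.1 defines the Dose 4 population as "Subjects receiving Dose 4 and having safety data between Dose 4 and 6 months after Dose 4".

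On attrition, Protocol Section 3.3 says "Assuming a 15% dropout rate, approximately 200 subjects would be evaluable for immunogenicity" and "Subjects who withdraw or are withdrawn from the study after randomization will not be replaced, regardless of the reason for withdrawal". Protocol Section 3.1 says "Each subject will participate in the study for approximately 16 months".

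**The concern.** Read together, these sections suggest a mismatch. Table 4 uses everyone randomized, yet one set of primary endpoints can be observed only in infants who stay in the study for about ten months and receive Dose 4. Withdrawals are not replaced, and the protocol itself expects some loss. A reader who takes the 90% chance of seeing a 1% event as covering Dose 4 would be somewhat too optimistic.

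Keeping all 230 in the denominator would not remove the point, because an infant who never receives Dose 4 cannot have a reaction to it. The table is also the only design property offered for the primary objective, and the results are meant to inform Phase 3. What is at stake is how much reassurance to draw from seeing no cases of a rare reaction after the fourth dose.

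**Working it through.** **Inputs.** 230 per arm and true rates of 0.5%, 1% and 5% (Protocol 9.1); 15% dropout and about 200 evaluable (Protocol 3.3); about 16 months of participation (Protocol 3.1); Dose 1 at 2 months and Dose 4 at 12 months of age (Protocol 3), so Dose 4 falls about 10 months after entry.

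**Formula.** The probability of at least one event among N subjects at true rate p is 1 − (1 − p)^N.

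**The plan's own figures, N = 230.**
- p = 0.005: 1 − 0.995^230 = 0.6843
- p = 0.01: 1 − 0.99^230 = 0.9009
- p = 0.05: 1 − 0.95^230 > 0.999

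All three agree with Table 4.

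**Reading the 200 in Section 3.3.** 230 × 0.85 = 195.5, whereas 460 × 0.85 = 391. The 200 is therefore a rounded figure per arm, and the missing words are a clerical slip.

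**Dose 4 with fewer contributors.** The documents do not say how many infants will be lost before Dose 4, so the loss is an assumption shown as a range. Fractions of a subject are rounded down.

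| Assumed position at Dose 4 | N per arm | p = 0.5% | p = 1% |
|---|---|---|---|
| No loss (Table 4) | 230 | 0.684 | 0.901 |
| 5% lost | 218 | 0.665 | 0.888 |
| 15% accruing evenly over 16 months | 208 | 0.648 | 0.876 |
| 10% lost | 207 | 0.646 | 0.875 |
| Protocol's rounded evaluable number | 200 | 0.633 | 0.866 |
| Full 15% lost before Dose 4 | 195 | 0.624 | 0.859 |

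The even-accrual row uses 15% × 10/16 = 9.4%, and 230 × 0.90625 = 208.4. At p = 5% the probability stays above 0.999 in every row.

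**Size of the gap.** At N = 195 the fall is 0.6843 − 0.6237 = 6.1 points at the 0.5% rate and 0.9009 − 0.8591 = 4.2 points at the 1% rate. At 5% loss it is 2.0 and 1.3 points. The chance of missing a 1% event rises from 0.99^230 = 9.9% to 0.99^195 = 14.1% at the far end of the range.

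**Effect on what is reported.** With no events, the exact upper 95% limit is 1 − 0.025^(1/N), which is 1.59% at N = 230 and 1.87% at N = 195. The analysis will use the actual N, so the reported limit already carries the loss.

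**Where 230 is the right planning number.** Setting aside infants randomized but never vaccinated or without safety data, it fits:
- Dose 1 reactions;
- AEs from Dose 1 to one month after Dose 3, which SAP 4.1 and 6.1.3.1 analyse in recipients of Dose 1 with safety data;
- SAEs and newly diagnosed chronic conditions through six months after Dose 4, in the safety population (SAP 6.1.4.1);
- reactions compiled across all four doses (Protocol 9.4).

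For the intervals that run past Dose 1, some follow-up will be lost, so the fit is close and not exact.

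**The case for a change.** The strongest case for changing the table is that the direction of the error does not depend on any assumption about timing. Any loss before Dose 4 lowers the probability, and the protocol plans for loss. A table that names all three event types without limiting its scope invites the wrong reading, and a label with one extra row would be cheap.

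The first part stands: fewer than 230 per arm will very probably contribute to Dose 4, and Section 9.1 does not say so. The remedy does not follow, for three reasons.

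- **The table is conditional on its N.** It states N=230 in the sentence and in the row label and gives no figure for Dose 4, so no printed number is wrong. The dropout assumption is in the same protocol for anyone who wants to apply it.
- **The 15% is not a planned loss before Dose 4.** Section 3.3 ties it to being evaluable for immunogenicity. Under Protocol 9.2 that status also depends on blood-draw timing, an assay result, prohibited vaccines and major deviations. An infant can fail those criteria and still supply Dose 4 safety data. A row at 195 would write into the protocol a worst-case timing that the sponsor never stated.
- **Relabelling would make the table less accurate.** Confining the 230 row to Dose 1 would take it away from the other summaries that it fits, and would leave Doses 2 and 3 with no row.

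Nor is the change free. It is a protocol amendment, which needs ethics approval under Protocol Section 12.1.

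**Conclusion.** No change is needed. Table 4 is correct for 230 contributing infants per arm. What Section 9.1 leaves unsaid, that later doses will have fewer contributors, is a matter of scope that a statistician fills in from Section 3.3. If 5% to 15% are lost before Dose 4, the probability of seeing at least one event is about 2 to 6 points lower at a true rate of 0.5% and about 1 to 4 points lower at 1%. At 5% it is unchanged. Those figures rest on assumed losses, because the protocol gives no timing for dropout.

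Nothing downstream depends on the table. SAP Section 5.1 rules out hypothesis tests and formal decision rules. SAP Sections 5.2.1, 6.1.1 to 6.1.3 give each Dose 4 proportion its own numerator, denominator and Clopper-Pearson interval. Anyone judging a rare Dose 4 reaction will read that interval, whose upper limit with no events would move only from 1.6% to 1.9% across the full range considered. A footnote saying that the table assumes 230 contributors would do no harm if Section 9.1 were reopened for another reason, but it does not justify an amendment.

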## 9.2. Analysis Populations

The safety population will include all subjects who receive 1 dose of 20vPnC or 13vPnC. Subjects will be assigned to vaccine groups corresponding to the vaccine actually received. The safety population will be the only analysis population for the primary endpoints.

The Dose 3 evaluable immunogenicity population will include any subject:

- 1. Who was eligible for the study.
- 2. Who was randomly assigned to receive the vaccine.
- 3. Who was 42 to 98 days of age, inclusive, on the day of first vaccination.
- 4. Who received the vaccine to which he or she was randomly assigned at all 3 doses.
- 5. Who had an IgG concentration for at least 1 serotype after Dose 3.
- 6. Whose blood collection was within 28 to 42 days, inclusive, after Dose 3.
- 7. Who received no prohibited vaccines before the blood draw after Dose 3.
- 8. Who had no other major protocol deviations as determined by the clinician or medical monitor.

Additional criteria are described in the SAP. The Dose 3 evaluable immunogenicity population will be the primary analysis population for immunogenicity results from the blood collected 1 month after Dose 3.

The Dose 4 evaluable immunogenicity population will include any subject:

- 1. Who was eligible for the study.
- 2. Who was randomly assigned to receive the vaccine.
- 3. Who was 42 to 98 days of age, inclusive, on the day of first vaccination.
- 4. Who received the assigned vaccine, as randomized, within the defined window for Dose 4 (365-386 days of age; see Schedule of Activities).
- 5. Who received the vaccine to which he or she was randomly assigned at all 4 doses.
- 6. Who had an IgG concentration for at least 1 serotype after Dose 4.
- 7. Whose blood collection was within 28 to 42 days, inclusive, after Dose 4.
- 8. Who received no prohibited vaccines before the blood draw after Dose 4.
- 9. Who had no other major protocol deviations as determined by the clinician or medical monitor.

[figure not shown]
Additional criteria are described in the SAP. The Dose 4 evaluable immunogenicity population will be the primary analysis population for immunogenicity results after Dose 4.

### 9.3. Immunogenicity Analysis

All serotypes will be analyzed in the same way. All endpoints will be summarized by vaccine group.

The Luminex assay IgG concentration of 0.35 µg/mL will be used as the predefined IgG

reference concentration for all serotypes, with the exception of serotypes 5 (0.23  $\mu g/mL$ ), 6B (0.1  $\mu g/mL$ ), and 19A (0.12  $\mu g/mL$ ). The 95% CIs will be obtained using the Clopper-Pearson method.

[figure not shown]
# 9.4. Safety Analysis

All safety analyses will be performed using the safety population.

Descriptive statistics for local reactions and systemic events from Day 1 to Day 7 will be presented by severity and cumulatively across severity levels. Descriptive statistics will include proportions of subjects with the indicated endpoint and the associated Clopper-Pearson 95% CIs. Vaccine groups will be compiled separately.

Descriptive statistics for local reactions and systemic events will be compiled separately for each dose. The same descriptive statistics will be compiled across all 4 doses.

AEs (including nonserious AEs, SAEs, and NDCMCs) will be compiled over 2 intervals: from Dose 1 to 1 month following Dose 3 and from Dose 4 to 1 month following Dose 4. SAEs and NDCMCs will be summarized from Dose 1 until 6 months after Dose 4. The descriptive statistics for AEs will be summarized as the number and percentage of subjects reporting at least 1 event of each preferred term with the associated Clopper-Pearson 95% CIs, arranged by system organ class.

## 10. QUALITY CONTROL AND QUALITY ASSURANCE

Pfizer or its agent will conduct periodic monitoring visits during study conduct to ensure that the protocol and GCPs are being followed. The monitors may review source documents to confirm that the data recorded on CRFs are accurate. The investigator and institution will allow Pfizer monitors/auditors or its agents and appropriate regulatory authorities direct access to source documents to perform this verification. This verification may also occur after study completion.

During study conduct and/or after study completion, the investigator site may be subject to review by the investigational review board (IRB)/ethics committee (EC), and/or to quality assurance audits performed by Pfizer, or companies working with or on behalf of Pfizer, and/or to inspection by appropriate regulatory authorities.

The investigator(s) will notify Pfizer or its agents immediately of any regulatory inspection notification in relation to the study. Furthermore, the investigator will cooperate with Pfizer or its agents to prepare the investigator site for the inspection and will allow Pfizer or its agent, whenever feasible, to be present during the inspection. The investigator site and investigator will promptly resolve any discrepancies that are identified between the study data and the subject's medical records. The investigator will promptly provide copies of the inspection findings to Pfizer or its agent. Before response submission to the regulatory authorities, the investigator will provide Pfizer or its agents with an opportunity to review and comment on responses to any such findings.

It is important that the investigator(s) and their relevant personnel are available during the monitoring visits and possible audits or inspections and that sufficient time is devoted to the process.

#### 11. DATA HANDLING AND RECORD KEEPING

## 11.1. Case Report Forms/Electronic Data Record

As used in this protocol, the term CRF should be understood to refer to either a paper form or an electronic data record or both, depending on the data collection method used in this study.

A CRF is required and should be completed for each included subject. The completed original CRFs are the sole property of Pfizer and should not be made available in any form to third parties, except for authorized representatives of Pfizer or appropriate regulatory authorities, without written permission from Pfizer.

The investigator has ultimate responsibility for the collection and reporting of all clinical, safety, and laboratory data entered on the CRFs and any other data collection forms (source documents) and ensuring that they are accurate, authentic/original, attributable, complete, consistent, legible, timely (contemporaneous), enduring, and available when required. The CRFs must be signed by the investigator or by an authorized staff member to attest that the data contained on the CRFs are true. Any corrections to entries made in the CRFs or source documents must be dated, initialed, and explained (if necessary) and should not obscure the original entry.

In most cases, the source documents are the hospital or the physician subject chart. In these cases, data collected on the CRFs must match the data in those charts.

In some cases, the CRF may also serve as the source document. In these cases, a document should be available at the investigator site and at Pfizer that clearly identifies those data that will be recorded on the CRF, and for which the CRF will stand as the source document.

